#### Study Periods:

**Baseline Monitoring Period:** During this phase (6 months), PPE compliance will be audited by trained observers. Aggregate compliance reports with comparison to peer units will be fed back to unit leadership for dissemination among unit HCP.

Awareness and Accountability Period: Following the Baseline Monitoring Period an added facet of the program will be implemented with the intent of further improving PPE compliance. During this phase (6 months), PPE compliance will be audited using similar procedures to the baseline period. Two added measures will also be implemented: real-time reminders of lapses in PPE use by the trained observers and a tiered accountability model for feedback of compliance data (described below). Observers will be trained on how to provide professional feedback in real-time when lapses or noncompliance are identified.

**Tiered Accountability Model for Feedback of Compliance Data:** As a part of the observation process, tiered interventions that follow the model that has been used at Vanderbilt for several years to improve performance on multiple process and outcome measures, including hand hygiene, will be implemented. The tiered intervention model operates under the assumption that the vast majority of professionals will respond to data and improve

performance. However, for some, additional interventions are needed to facilitate high performance. The steps of the tiered intervention (a.k.a. "accountability pyramid") are described in detail below (Figure 4).

[figure not shown]
*Monitoring and Feedback:* This tier of the intervention will be implemented as part of the Baseline Monitoring period and continue into the Awareness and Accountability Period. During this phase, we will provide ongoing PPE compliance data to unit leader/quality management teams, including their performance relative to internal peers. We will reinforce their performance through positive messages from the study team and will ask them to share their best practices so that we may disseminate to other units for problem solving.

During the Awareness and Accountability Period, two additional tiers will be included.

1) Awareness: If a unit performs below target compliance goals for two or more periods, the unit leadership will receive written/electronic communication regarding the unit's below target performance (see Sample Compliance Awareness Report, Appendix) and will be provided information about resources available to improve performance, including local peers/units who are engaged in best practices. To allow units ample opportunity to demonstrate improvement, they may receive up to two awareness intervention visits before escalation to the next level.

2) *Guided Engagement:* If performance does not improve after two awareness interventions, units will receive a guided intervention, which includes in-person sharing of performance and meaningful comparisons delivered by trained study personnel.

**Analysis:** The aggregate rates of PPE compliance will be compared between both study periods, with a null hypothesis that compliance will not significantly improve from the Baseline Monitoring Period to the Awareness and Accountability Period. The primary analysis will examine the aggregate compliance in all study units, with an additional analysis stratified by acute care facility. In addition, a more robust interrupted time-series regression analysis with Newey-West standard errors will be performed using bimonthly compliance rates.

**Limitations:** Even with a robust observation program, the number of instances of HCP PPE use observed will be only a small proportion of the total number of these opportunities. Compliance measurements from the observed events may not be representative of the total, as there may be a Hawthorne Effect on HCP compliance based on the presence of an observer. We have encountered this issue with the hand hygiene program as well. Because these interventions and programs are designed to alter HCP behavior, we have found that even with the Hawthorne Effect of direct observation, the provision of regular observation and real-time feedback when lapses are noted has led to a hardwiring to expected behavior (based on other measures of hand hygiene compliance such as patient and embedded observer reports). We

anticipate a similar effect with the designed observation program. Finally, because the success of the hand hygiene program is due in part to the institutional culture at VUMC surrounding quality and to the shared goal of pursuing a robust and reliable quality and safety culture, any impact identified in our study will need to be examined in other settings, including those where such a culture is not as mature or robust.

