As guided by the studies noted above, the findings from events such as the outbreak of SARS among HCP and the HCP-acquired EVD cases, and the experience of healthcare epidemiologists and infection preventionists working in the field, there are likely many factors that can impact the effectiveness of PPE (Figure 1). Starting with determining the necessity of PPE use for a given patient care scenario and continuing through PPE selection, donning (or "putting on"), use, and doffing (removal), opportunities for breaches in PPE use and subsequent exposure of HCP to infectious pathogens are considerable.

[figure not shown]

Figure 1: Factors that may Impact the Effectiveness of PPE among HCP

Determining whether a specific patient requires placement into precautions upon entry to the healthcare facility is essential, and failure to recognize the need for precautions can lead to HCP exposure to pathogens of concern. The number of patients in a given unit may also impact PPE compliance. Vanderbilt investigators ([name]) collaborated on the study by Dhar *et al* that noted a negative impact on compliance with PPE use (from 31.5% to only 6.5%) and hand hygiene (from 43.6% to 4.9%) as the proportion of patients on isolation precautions increased from less than 20% to greater than 60%.

Once patients are placed into precautions, factors affecting PPE effectiveness include the availability of PPE, the perception of HCP risk (i.e. HCP belief of a specific patient's true likelihood of infection with the suspected pathogen), and the construction of the PPE (in terms of ease of use as well as underlying materials). Failure to don the PPE correctly, whether due to lack of HCP training on PPE use, the urgency of the patient care duty to be performed (i.e. emergent vs. routine), or physical constraints (i.e. enough space to don attire), also may impact PPE effectiveness. Patient factors (including clinical symptoms), details about the patient care tasks (i.e. duration, complexity), and tolerability of the PPE are also important. Finally, failure to doff PPE correctly can lead to contamination of HCP and the environment.

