#### Study Procedures:

**Study Outcomes:** Overall compliance with PPE use for patients placed in transmission-based precautions.

**Data Collection:** Trained observers will utilize the revised audit tool to capture compliance. A target of 500 observations of individual HCP PPE use events will be collected per month per study unit. This will provide ~42,000 observations for each study period (500 observations/month/unit \* 6 months \* 14 units). These observers will be formal Vanderbilt Epicenter personnel as well as unit and clinic HCP, modeled after the Vanderbilt Hand Hygiene Program described above. Observers will be trained on the use of the tool in a standardized fashion.

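### Aim II compares PPE compliance between two consecutive half-years with no stated plan to record or adjust for the share of patients on precautions, which the protocol itself links to compliance

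*Protocol*

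**What the plan says.** The outcome in Protocol, Specific Aim II, Study Procedures, is "Overall compliance with PPE use for patients placed in transmission-based precautions". Observers work to a quota: "A target of 500 observations of individual HCP PPE use events will be collected per month per study unit". The protocol then states: "This will provide ~42,000 observations for each study period".

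Under Study Periods, a six-month baseline with audit and aggregate feedback comes first. The second six months add real-time reminders and tiered accountability: "Following the Baseline Monitoring Period an added facet of the program will be implemented". No unit is held back as a concurrent control.

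The Analysis paragraph sets the main contrast: "The aggregate rates of PPE compliance will be compared between both study periods". It continues: "The primary analysis will examine the aggregate compliance in all study units, with an additional analysis stratified by acute care facility". It also plans that "a more robust interrupted time-series regression analysis with Newey-West standard errors will be performed using bimonthly compliance rates". No covariate is named for any of these analyses. The Limitations paragraph covers the small fraction of events observed, the Hawthorne effect and institutional culture, but not isolation burden.

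In the Significance section, where factors affecting appropriate PPE use are discussed, the protocol says the number of patients in a unit may affect compliance. It cites a multicentre study with the investigators' participation in which PPE compliance went from 31.5% to 6.5% "as the proportion of patients on isolation precautions increased from less than 20% to greater than 60" per cent.

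**The concern.** The protocol identifies a factor associated with its own Aim II outcome, then sets up a before-after comparison in which that factor can vary freely. The contrast attributes to reminders and accountability whatever differs between two half-years.

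Consecutive half-years cannot be matched for season. Table 1 lists seasonal influenza under Droplet Precautions, and 6 of the 14 target units are in a children's hospital, so a seasonal change in the number of isolated patients is plausible. Aim III adds preemptive Contact Precautions on six units of the same adult hospital that supplies six Aim II units. Whether units or dates overlap cannot be read from the document, so this is only a possibility.

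If the share on precautions fell in the second period, compliance could rise with no intervention effect. If the share rose, a real gain could be masked. A bias of this kind does not shrink as more observations are collected.

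**Working it through.** **The protocol's own figure.** 500 observations × 6 months × 14 units = 42,000 per period, as stated. Aim II states no target effect, power or significance level, so there is no power figure to reproduce.

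**Slope implied by the cited study.** The fall is 31.5 − 6.5 = 25 percentage points. The protocol gives only the bands (under 20%, over 60%), so the distance in isolation share must be assumed, along with linearity:

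| Assumed distance | Basis | Compliance points per point of share | Effect of a 5-point change |
|---|---|---|---|
| 40 | band edges, 20% to 60% | 25/40 = 0.63 | 3.1 |
| 70 | band midpoints, 10% to 80% | 25/70 = 0.36 | 1.8 |
| 100 | full range, 0% to 100% | 25/100 = 0.25 | 1.25 |

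The 5-point change is itself an assumption. A 2-point change would give 0.5 to 1.25 points and a 10-point change 2.5 to 6.3 points.

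**Naive precision.** Assume compliance near 75%, close to the 74.3% gown compliance implied by the 25.7% noncompliance in the same cited study, and treat all observations as independent:

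- SE = 100 × √(2 × 0.75 × 0.25 / 42,000) = 0.30 points.
- Difference detectable with 80% power at two-sided 5% (both assumed) = (1.96 + 0.84) × 0.30 = 0.84 points.

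**Precision allowing for clustering.** Each unit contributes 500 × 6 = 3,000 observations per period. With an assumed within-unit-period correlation of 0.01:

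- Design effect = 1 + 2,999 × 0.01 = 31.
- SE = 0.30 × √31 ≈ 1.7 points.
- A shift of 1.25 to 3.1 points is then about 0.8 to 1.9 standard errors.

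**What the other planned analyses can do.**

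- *Facility strata.* These separate hospitals from one another. Within each hospital the contrast is still first half-year against second, so a change in share over time remains.
- *Interrupted time series.* A trend term can absorb a smooth drift. With no term for isolation share, a step near the phase boundary is read as an intervention effect. One year of data cannot separate season from period.

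**The case against.** The strongest reply is that covariates for a before-after comparison are commonly left to a statistical analysis plan, which is not shown. The protocol does not call the comparison unadjusted, and the audit tool has yet to be developed, so its fields are unknown. A reader might infer that the share will not be recorded or that adjustment is ruled out. The text supports neither; it only says nothing about either. The point survives because the protocol does fix the primary contrast as pooled aggregate compliance between periods, and because Aim III names factors to be measured and included while Aim II has no counterpart.

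The size is also open to challenge. The cited contrast is observational, compares extreme bands across centres, and is not shown to describe change within a unit over time. The same study is quoted with 25.7% gown and 19.9% glove noncompliance, so 31.5% and 6.5% probably reflect a stricter measure, and the slope may not carry over to Aim II's overall compliance. The documents give no reason to expect a 5-point change in share. All of this stands, and it limits the calculation to an illustration.

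Stable differences in share between units largely cancel if the same 14 units are observed in both periods. That also stands, but it does not deal with change over time.

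**Conclusion.** The point holds as a design weakness worth correcting before Aim II starts. The primary comparison is open to a time-varying confounder that the protocol itself describes, and no planned analysis, as written, would remove a step or seasonal change in it. The direction is unknown.

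The size is unknown too. The range of 1.3 to 3.1 points for a 5-point change rests on linearity, on an assumed distance of 40 to 100 points between bands, and on the cited slope applying to Aim II's measure.

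A reader might divide that range by the naive standard error and conclude that the result would be wrong by roughly 4 to 10 standard errors. The documents do not support this, because it treats 84,000 observations clustered in 14 units as independent. With a correlation of only 0.01 the ratio falls to about 0.8 to 1.9. Clustering reduces the apparent significance of the bias but not the bias itself.

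**What to change.** For each unit and half-month, extract the share of patient-days under transmission-based precautions from routine census data or precaution orders. Report it by period. Include it as a covariate in a unit-level between-period model and in the interrupted time series, and show every estimate with and without it. If orders cannot be extracted, observers can note the number of isolated patients on the unit at each audit; that field would have to be in the tool before baseline begins.

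The cost is one data extract and one model term, with some loss of precision. Aim III equates the same bimonthly interval with 12 points per period, so the Aim II series would be short, and a covariate that tracks season or period will widen the interval.

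A reader might assume that adjustment cannot remove any of the intervention effect because the programme does not decide who is isolated. That is not guaranteed: the protocol's premise is that better PPE use reduces transmission, which could lower later isolation burden. The pathway is probably small over six months, but it is the reason to present both adjusted and unadjusted estimates.

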#### Implementation Study:

**Study Population:** The initial implementation will occur on acute care inpatient units at Vanderbilt University Hospital (VUH), the Monroe Carell Jr. Children's Hospital at Vanderbilt (MCJCHV), and Williamson Medical Center (WMC). The target number of units will be 6 VUH, 6 MCJCHV, and 2 WMC units. All HCP on study units will be included for observation of practice.

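### Aim II's primary analysis is a pooled before/after rate that provides for neither baseline trend nor unit-by-period variation, while the planned time-series model is only additional

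*Protocol*

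**What the plan says.** The setting is the Implementation Study of Specific Aim II. On its size, the protocol says "The target number of units will be 6 VUH, 6 MCJCHV, and 2 WMC units" and, under Data Collection, "A target of 500 observations of individual HCP PPE use events will be collected per month per study unit". From these it concludes: "This will provide ~42,000 observations for each study period".

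The Analysis paragraph under Study Periods says "The aggregate rates of PPE compliance will be compared between both study periods" and then ranks the analyses: "The primary analysis will examine the aggregate compliance in all study units", while a stratified analysis is additional. The stratification is by facility (three), not by unit (14). The same paragraph adds an interrupted time-series regression with Newey-West errors on bimonthly rates. It describes that analysis as the more robust of the two, but places it in addition to the primary one. No test, variance method, alpha or target difference is given for the primary comparison.

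For the Baseline Monitoring Period the protocol says "Aggregate compliance reports with comparison to peer units will be fed back to unit leadership". Of the monitoring-and-feedback tier it says "This tier of the intervention will be implemented as part of the Baseline Monitoring period", and that tier continues into the second period. The second period adds two measures: real-time reminders, and the tiered accountability model with its two further tiers, awareness and guided engagement. The protocol's stated premise is that most professionals improve when shown data, and the second period is meant to improve compliance further.

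**The concern.** Two features of the design do not fit a comparison of two pooled proportions.

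First, on the protocol's own premise, feedback in baseline should already be raising compliance. A difference between two six-month means cannot separate a continuation of that rise from the effect of the added measures. The analysis that can separate them is planned, but it does not carry the primary conclusion.

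Second, the intervention acts on units: escalation is triggered by a unit's performance and delivered to its leadership. Each unit supplies about 3,000 observations per period. If unit compliance moves between periods for local reasons (staffing, case mix, observers), the information on the change comes from 14 units rather than 84,000 observations.

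At stake is what a positive primary result would mean. It could reflect continuing feedback or ordinary unit-level movement, yet be read as evidence for the accountability tiers, in a programme that the protocol hopes to extend to many kinds of facility.

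**Working it through.** **Inputs from the protocol.** 500 observations per unit per month, 6 months per period, 6 + 6 + 2 = 14 units.

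**Assumptions.** Compliance p = 74.3%, which is 100% minus the 25.7% gown noncompliance quoted in the Significance section (range tried: 50% to 90%). Two-sided alpha 0.05. A pooled two-proportion z-test on independent observations. The monthly slope s and the unit-by-period SD τ are not in the protocol and are shown as ranges.

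**The plan's own figure.** 500 × 6 × 14 = 42,000 per period, which agrees. Per unit and period: 500 × 6 = 3,000.

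**Pooled standard error.** √(2 × 0.743 × 0.257 / 42,000) = 0.00302, or 0.30 points. The significance threshold is 1.96 × 0.302 = 0.59 points (0.41 at 90% compliance, 0.68 at 50%). The difference detectable with 80% power is (1.96 + 0.84) × 0.302, about 0.84 points.

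**Trend, with no added effect.** Under a steady slope s, the midpoints of the two periods are 6 months apart, so the means differ by 6s. With τ = 0, the chance that the pooled test is significant is:

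| s (points/month) | 6s (points) | Pooled test significant |
|---|---|---|
| 0.05 | 0.3 | 17% |
| 0.1 | 0.6 | 51% |
| 0.2 | 1.2 | 98% |
| 0.25 | 1.5 | 99.9% |
| 0.5 | 3.0 | about 100% |

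If the rise stopped exactly at the end of baseline, the baseline mean would lie 3s above the start and the second period 6s above it. The means would still differ by 3s.

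**Unit-by-period variation, with no trend.** Variance of the difference = 2p(1−p)/42,000 + 2τ²/14. Dividing by the first term gives the design effect 1 + 3,000τ²/[p(1−p)]. For τ = 2 points: 1 + 3,000 × 0.0004 / 0.191 = 7.28. The true type I error of the pooled test is 2[1 − Φ(1.96/√design effect)].

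The formula was checked by simulation: 20,000 runs, 14 units × 3,000 observations per period, and stable unit differences with an SD of 10 points. The comparator is a paired t-test on the 14 unit differences.

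| τ (points) | Design effect | Effective n per period | Pooled type I, formula | Pooled type I, simulated | Paired t, simulated | Detectable difference, 80% power |
|---|---|---|---|---|---|---|
| 0 | 1.0 | 42,000 | 5.0% | 4.3% | 5.1% | 0.84 |
| 1 | 2.57 | 16,336 | 22.2% | 21.0% | 4.6% | 1.35 |
| 2 | 7.28 | 5,766 | 46.8% | 46.1% | 4.9% | 2.28 |
| 3 | 15.14 | 2,774 | 61.4% | 61.7% | 5.0% | 3.29 |
| 5 | 40.28 | 1,043 | 75.7% | 75.6% | 5.1% | 5.36 |

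The first row shows that stable differences between units do no harm: the same units appear in both periods with equal target counts, so those differences cancel.

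**Both together, simulated with τ = 2 points and no added effect.** At slopes of 0.1, 0.25 and 0.5 points per month the pooled test rejects in 57%, 87% and 99.8% of runs. The paired t-test rejects in 10.5%, 41% and 93%. The paired test cures the clustering problem but not the trend.

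**The case against.** The strongest reply is that the protocol already commits to the right analysis. The interrupted time series models trend and serial correlation, works on rates rather than individual observations, and is acknowledged in the text to be the stronger method. A facility-stratified analysis is planned as well. This stands: trend is not overlooked, and the fault lies in the ranking. A reader who infers that the plan has no safeguard against trend goes further than the text allows.

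It can also be said that the primary paragraph names no test, so a cluster-adjusted one could be set in a statistical analysis plan not seen here. That stands too, and the error rates above are therefore conditional on an independent-observations test. But a better variance would not remove the trend, and the protocol itself fixes which comparison is primary.

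A reader might infer that with 42,000 observations per period significance is almost guaranteed. The documents do not support that. With neither trend nor unit-by-period variation the error stays at 5%. Variation alone, at an SD of 1 to 5 points, gives roughly 20% to 75%. Near-certainty needs a continuing trend, and the protocol gives no figure for either quantity. Nor does repeated observation within 14 units inflate the error merely because units differ from one another.

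Finally, the protocol does disclose that the second period adds measures to a programme already running. What the comparison estimates is therefore a matter of labelling, not of concealment.

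**Conclusion.** The point holds as a defect of ranking and specification. As written, the primary conclusion rests on a difference of period means that cannot separate the added measures from a rise that the protocol itself expects feedback to produce, and no provision is stated for unit-by-period variation.

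That the means separate by 6s under a steady slope is arithmetic and does not depend on which test is used. The rest is conditional. With independent observations at about 75% compliance, and units otherwise stable, a slope of about 0.2 points per month is almost always significant. Without a trend, an assumed unit-by-period SD of 1, 2 or 3 points gives a type I error of about 22%, 47% or 62%. Slope and SD are assumptions; the protocol supports the expected direction of the trend but not its size.

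**What to change.** Make the planned segmented time-series model the primary analysis, with terms for baseline trend, change in level and change in slope. Fit it to unit-by-half-month compliance rates, with unit and unit-by-period variation. Aim III equates bimonthly rates with 12 points per six-month period, so on the same reading Aim II would have 14 × 24 = 336 unit-level rates of about 250 observations each.

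Keep the pooled rate as description. A paired contrast of the 14 units may be supportive but should not be primary, because it leaves the trend in.

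State that the estimate is the added effect of real-time reminders and the two further tiers over audit with feedback, not the effect of the whole programme.

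The change needs new protocol wording and a little more analysis work, but no change to design or data collection. The price is wider confidence intervals: at an assumed SD of 2 points, even before a trend is estimated, the detectable difference rises from 0.84 to about 2.3 points. A linear baseline trend may also understate the effect if the rise would have levelled off by itself, so a sensitivity analysis on the form of the trend is advisable.
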